8.0 Study Endpoints

8.1 Primary and secondary study endpoints.

We selected brachial artery FMD as an endpoint because unacylated ghrelin increases brachial artery FMD within hours of intravenously administered unacylated ghrelin (8). This immediate effect on brachial artery FMD provides a short-term therapeutic endpoint for identifying an optimal unacylated ghrelin dose. The brachial artery FMD will be measured at baseline and at six or 8-12 hours after each dose of unacylated ghrelin is administered.

Additional endpoints for this pilot study include a) circulating levels of unacylated ghrelin; b) levels of acylated ghrelin; c) biomarkers of inflammation.

8.2 Primary or secondary safety endpoints.

Unacylated ghrelin has been administered intravenously to more than 70 humans without any serious adverse effects (4,8-14). Two participants in one study experienced mild facial swelling after receiving unacylated ghrelin intravenously (14). Symptoms resolved within hours (14). Dizziness was reported in one study in which intravenous acylated and unacylated ghrelin were administered simultaneously over the short term (12). However, this adverse effect was not observed when unacylated ghrelin was administered alone (12). We will monitor participants for symptoms of facial swelling and dizziness. We will monitor participants for blood pressure and signs of facial swelling. An electrocardiogram will be obtained at visit 1 and before the 20 ug/kg and 40 ug/kg injections and 24 hours after each injection. Renal function, liver function, electrolytes, and CBC will be obtained at baseline, before the 20 ug/kg and 40 ug/kg injections, and approximately 24 hours after each injection.

9.0 Procedures Involved

9.1 Study design.

STUDY OVERVIEW. We will identify the lowest subcutaneous dose of unacylated ghrelin that maximizes brachial artery flow mediated dilation (FMD). These PAD participants will receive three different subcutaneous doses of unacylated ghrelin on three different days and will undergo measurement of unacylated ghrelin levels prior to the injection and at specified time intervals. Each dose will be separated by a wash-out period of \geq one week. Data will be obtained for all six participants at each dose before moving to the next dose. We will test doses of 10 ug/kg, 20 ug/kg, and 40 ug/kg of unacylated ghrelin on three separate days for each participant. These doses were selected based on published literature and the experience of our consultants [name], who has an ongoing study of intravenously administered unacylated ghrelin in healthy

PROTOCOL TITLE: Unacylated Ghrelin to Improve Functioning in PAD: the GIFT Trial

people (R01-DK097550) and [name], who has an ongoing study of subcutaneously administered acylated ghrelin in older frail people without PAD (R21-AG040488).

(See Section 7.0 above). Justification for proposed doses of unacylated ghrelin. Unacylated ghrelin is a synthetic 28 amino-acid protein. The $\frac{1}{2}$ life of intravenously administered unacylated ghrelin is 30-34 minutes, which is comparable to but slightly longer than the $\frac{1}{2}$ life of insulin and glucagon (9). In comparison, the $\frac{1}{2}$ life of intravenously administered acylated ghrelin is 9 to 11 minutes (9). A portion of intravenously administered acylated ghrelin is converted to unacylated ghrelin (9). In contrast, unacylated ghrelin is not converted to acylated ghrelin (9). In healthy people, circulating levels of unacylated ghrelin are higher than those of acylated ghrelin, in a ratio that is typically 4:1 but ranges from 2:1 to 9:1 (9,11,48). In a study of healthy people, a 4X higher dose of intravenously administered unacylated ghrelin achieved a CMax that was twelve times higher than that for intravenously administered acylated ghrelin (9). Because of the longer $\frac{1}{2}$ life of unacylated ghrelin and the substantially greater CMax achieved with unacylated ghrelin as compared to acylated ghrelin, we will begin with a subcutaneous unacylated ghrelin (10 ug/kg) dose that is comparable to that selected by [name] for her study of subcutaneously administered acylated ghrelin. Next, we will test a subcutaneous dose of unacylated ghrelin that is 2X the starting dose (20 ug/kg). Finally, we will test a subcutaneous dose of unacylated ghrelin that is 4X times the starting dose (40 ug/kg). Four times the starting dose was selected as the maximal dose to test because circulating levels of unacylated ghrelin are approximately four times higher than circulating levels of acylated ghrelin and because of the higher CMax of unacylated as compared to acylated ghrelin (9,11,48). Although the GIFT Trial will administer unacylated ghrelin subcutaneously, we anticipate that, similar to intravenous administration, the maximum concentration of unacylated ghrelin will be greater than that for acylated ghrelin.

Preparation of subcutaneous unacylated ghrelin. Synthetic unacylated ghrelin powder will be supplied by the CS Bio Company and prepared by Northwestern Hospital's pharmacy for subcutaneous injection, using methods successfully implemented by [name] for subcutaneously administered acylated ghrelin.

Selecting the dose of unacylated ghrelin for future study. We will select the lowest subcutaneous dose of unacylated ghrelin that maximizes brachial artery FMD and minimizes circulating levels of oxidative stress. We will also use unacylated ghrelin levels to select the unacylated ghrelin dose. In selecting the dose, greater increases in brachial artery FMD and lower levels of oxidative stress will be prioritized over the level of unacylated ghrelin. For example, if the dose of 40 ug/kg results in substantially higher levels of unacylated ghrelin compared to the dose of 20 ug/kg, but improvement in brachial artery FMD is similar between the 20 ug/kg and the 40 ug/kg doses, then we will select a dose of 20 ug/kg for use in a possible future trial of unacylated ghrelin in PAD patients.

PROTOCOL TITLE: Unacylated Ghrelin to Improve Functioning in PAD: the GIFT Trial

9.2 Describe all research procedures.

Please see sections 7.0, 8.1, 8.2, and 9.1 above.

Ankle Brachial Index (ABI). After the participant rests supine for five minutes, the right brachial, dorsalis pedis (DP), posterior tibial (PT) and left DP, PT, and brachial artery pressures are measured using a hand-held Doppler probe. Pressures are measured twice. The ABI is calculated for each leg by dividing the average of the DP and PT pressures by the average brachial pressure.

Questionnaire Administration. Participants will be administered study questionnaires by a trained and certified health interviewer.

Brachial Artery Flow-Mediated Dilatation (FMD). Brachial artery imaging will be performed by a Registered Diagnostic Cardiac Sonographer according to established protocol (44,45). Changes in FMD will be read by [name] University of Wisconsin Atherosclerosis Imaging Research Program Core Laboratory by a single reader blinded to participant characteristics. We have more than a decade of experience working with [name] reading center (44,47,48). Measurement reproducibility in [name] laboratory has a median FMD difference of 0.02% (inter-quartile range: -0.03 to 0.04).

Six-minute walk. Participants will be asked to walk back and forth along a 100-foot hallway for six minutes. They will be instructed that the purpose of the six-minute walk test is to measure how long a distance they can walk in six-minutes. A script will be read to describe the study procedure. Participants will be asked whether they feel the test is safe to try and whether they have any questions. The six-minute walk is a well validated measure of walking endurance that predicts mobility loss and mortality in PAD populations (19,22,49,50) and improves in response to therapeutic interventions in older people with PAD (49-53). The intra-class correlation coefficient for the test-retest reliability of the six-minute walk test among 156 PAD participants in our SILC exercise trial was 0.90 ($p < 0.001$) when two six-minute walks were completed 1-2 weeks apart (51,54). Participants may be asked to perform the six-minute walk at baseline and may be asked to repeat it approximately four-eight hours after each subcutaneous ghrelin injection.

Four-Meter Walk. Participants are timed walking a four-meter distance in a corridor at their usual and fastest pace. Because of a learning effect, the four-meter walk is performed twice, and the fastest walk in each set is used in analyses. Participants are read a script by the study coordinator, describing the test. The test is demonstrated for the participant by the study coordinator- both at usual and at fastest pace. Participants may be asked to perform the four-meter walk at baseline and may be asked to repeat it approximately four-eight hours after each subcutaneous ghrelin injection.

PROTOCOL TITLE: Unacylated Ghrelin to Improve Functioning in PAD: the GIFT Trial

Blood pressure and pulse measurement. We will monitor blood pressure and pulse changes after the unacylated ghrelin injection. We will measure both sitting and standing blood pressure and pulse prior to the injections and at the intervals described above.

Electrocardiogram. An electrocardiogram will be obtained using standard procedures at baseline, prior to the 20 ug/kg and 40 ug/kg doses, and approximately 24 hours after each injection.

Blood collection. Participants will have approximately 300 mls of blood drawn over the course of the study to test levels of unacylated ghrelin and acylated ghrelin, inflammatory biomarkers, CBC, liver and kidney function, and electrolytes. Some blood will be stored for possible later analyses. At visits 2, 4, and 6 a peripheral intravenous line may be inserted for the purpose of obtaining blood samples more easily without multiple venipunctures.

9.3 Adequacy of protection against risks and methods to minimize potential risks. *Overview of protection against risks.* Prior to beginning data collection and study interventions, all study coordinators undergo training and are certified by [name] using a detailed checklist for each data collection element. Research coordinators are certified in each element of the study visit including obtaining informed consent, administering questionnaires, protecting confidentiality of collected data, performing the six-minute walk, and measuring the ABI. [name] re-certifies coordinators every six months to ensure continued adherence to protocol. Those not adhering to all aspects of the protocol undergo additional training followed by re-certification.

All research staff members have completed human subjects training required by Northwestern's institutional review board (IRB). This training includes education about the importance of maintaining confidentiality of personal health information. [name] or a co-investigator is available to answer questions that arise during the informed consent process as needed.

Participants are asked to sign a study consent form prior to data collection. The research coordinator reviews study procedures, including risks and benefits associated with study participation. The research coordinator answers participants' questions. [name] and other study investigators are available to answer participants' questions. Both the participant and the individual administering the consent form will sign the consent form. [name] pager, direct telephone line, and home telephone number are provided to participants.

Minimizing risks related to unacylated ghrelin. The six participants who receive the three injections of increasing doses of unacylated ghrelin will be observed at Northwestern Medical Center for approximately 8-12 hours after each injection. Participants will be observed for side effects. Participants will also return at 24-hour follow-up for assessment. The three injections will be separated by intervals

PROTOCOL TITLE: Unacylated Ghrelin to Improve Functioning in PAD: the GIFT Trial

of at least one week. Safety will also be monitored by our data safety monitoring board (DSMB) (see below).

Minimizing risk related to baseline and follow-up testing. All study coordinators undergo baseline training and are certified by [name] before beginning data collection. Training and certification involves ensuring that coordinators are trained in methods to help minimize falls. [name] re-certifies coordinators every six months to ensure continued adherence to study protocol. Those who are not adhering to protocol undergo additional training followed by re-certification.

Minimizing risk related to loss of confidentiality. The following methods will be employed to maintain confidentiality of participants. First, study recruitment letters will be mailed, using IRB-approved methods, only after receiving written permission from the participant's physician. The personal physician of each study participant will have the option of not allowing investigators to contact the potential participant. Lists of potentially eligible participants will be obtained by individuals who normally have access to these lists as part of their daily work requirements. Recruitment letters for potential participants identified from hospital and outpatient lists are prepared by research staff members whose job is to assist study investigators with recruitment. These research staff members have completed training in the ethical conduct of human subject research, including maintaining participant confidentiality. Recruitment letters to potential participants identified from medical center lists are mailed in sealed envelopes and addressed to the potential participant. All potential participants who receive mailed information about the study after the approval from their physician will have the opportunity to call a voice-mail system to ask not to be further contacted about this study. Secondly, only study investigators and key research staff will have access to the study database. Third, participants will be assigned a unique study identifier. Individual names will ultimately be removed from the study database and only the unique study identifier will be used to distinguish participants in the database. Fourth, collected data will be maintained in locked computer files and file cabinets to which only study investigators have access. Collected data will be used only for research purposes. Any published data will not contain any individual identifiers.

Data and Safety Monitoring Board (DSMB). We have identified three individuals: [name], Professor of Medicine at University of Colorado, [name], Professor of Endocrinology at the University of Illinois at Chicago, and [name], Professor of Statistics, University of Illinois at Chicago who have agreed to serve on the DSMB for the GIFT Trial. [name] is an internationally recognized expert in vascular medicine and is a board-certified cardiologist. [name] is an internationally recognized expert in endocrinology and is board certified in endocrinology. [name] is an internationally recognized statistician with expertise and experience with clinical trials and also missing data. All have provided letters of support, agreeing to

PROTOCOL TITLE: Unacylated Ghrelin to Improve Functioning in PAD: the GIFT Trial

participate in the GIFT Trial. The DSMB held their first meeting by telephone conference on Monday June 27, 2016. The DSMB will meet at least every six months during the study or more frequently as requested by the DSMB. The DSMB will convene by telephone conference call to review and approve the protocol prior to beginning data collection. The biostatisticians and data manager will work closely with the DSMB to perform interim analyses. Adverse events will be monitored continuously throughout the study and will be reported to the DSMB and IRB in a timely manner according to pre-specified requirements. Adverse event rates and interim study results will be reviewed and discussed by the DSMB at their regularly scheduled meetings. At least four categories of adverse events will be defined: a) Death; b) cardiovascular events (myocardial infarction, stroke, and coronary arrhythmias) c) lightheadedness/dizziness; d) swelling. We will report all hospitalizations to the DSMB in a timely fashion. We will use a designated data collection form to record these events and they will be reported to the Institutional Review Board according to local IRB requirements. They will be reported to the DSMB as required by the DSMB charter. As noted above, however, to date unacylated ghrelin has been found to have little to no toxicity in humans.

The purpose of this pilot study is to determine the potential therapeutic potential of subcutaneously administered unacylated ghrelin. The purpose is also to identify the most optimal dose of subcutaneously administered unacylated ghrelin for improving brachial artery flow-mediated dilation and reducing levels of inflammation in patients with PAD. An Investigational New Drug application to the FDA has been approved (IND# 130513).

We will use standardized questionnaires to collect data about each study participant. Please see attached data collection forms. We may use medical records to determine whether the patient was diagnosed with PAD prior to study enrollment.

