7.0 Study Timelines

Each participant's part in this study will last up to approximately six months.

Visit 1.

The initial visit will last approximately 2 hours. Informed consent will be provided and an ankle brachial index (ABI) measurement will be obtained to ascertain eligibility. Questionnaires will be administered to obtain information about their health and medical history. The six-minute walk test and the four-meter walking velocity at usual and fastest pace may be obtained. An electrocardiogram (ECG) will be performed and a blood sample will be obtained. Blood will be tested for liver and kidney function, electrolytes, and a complete blood count (CBC). A physical exam will be performed and medical history will be obtained. Height and weight will be measured. Vitals may be obtained. Vitals include blood pressure, heart rate, respiratory rate, temperature, and oxygen level.

Visits 2, 5, and 8.

Visits 2, 5, and 8 will last approximately 8-12 hours and will be separated by at least one week. We plan to collect data for each dose on all six participants before proceeding to the next dose. At visits #2, #5, and #8, respectively, participants will receive a subcutaneous injection of unacylated ghrelin of the following doses:

Visit 2: 10ug/kg

Visit 5: 20 ug/kg

Visit 8: 40 ug/kg

Prior to the injection. Prior to the injection, blood will be drawn and measured for levels of unacylated ghrelin and acylated ghrelin, inflammatory biomarkers, liver and kidney function, electrolytes, and CBC. Blood pressure and pulse will be obtained seated and in the standing position. Brachial artery flow-mediated dilation (FMD) will be measured.

30 minutes, 60 minutes, 90 minutes, and 3 hours and 6 hours post-injection.

A blood sample will be obtained and measured for levels of unacylated ghrelin and acylated ghrelin. Blood pressure and pulse will be obtained seated and in the standing position. A brachial artery FMD may be measured at 6 hours (e.g. if we do not see a change in brachial artery FMD 8-12 hours post-injection, we may want to move the collection time point to 6 hours).

8-12 hours post-injection. A blood sample will be obtained and measured for levels of unacylated ghrelin and acylated ghrelin as well as inflammatory markers.

PROTOCOL TITLE: Unacylated Ghrelin to Improve Functioning in PAD: the GIFT Trial

Blood pressure and pulse will be obtained seated and in the standing position. Brachial artery FMD may be measured.

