Additional vitals will be obtained at the discretion of the CRU nurse throughout the visit. Vitals include blood pressure, heart rate, respiratory rate, temperature, and oxygen level. Participants will be administered a questionnaire to assess symptoms. Participants may be asked to take their medications in the evening rather than the morning on the day of injection visits.

Participants may also be asked to repeat the six-minute walk and/or four-meter walks performed at baseline.

Visits 4 and 7.

At visits 4 and 7, a blood sample will be obtained and tested for liver and kidney function, electrolytes, and CBC. The physical exam and medical history may be repeated. Weight may be re-measured.

Visits 3, 6, and 9.

Visits 3, 6, and 9 will occur approximately 24 hours after the subcutaneous injections given at visits 2, 5, and 8, respectively. A blood sample will be obtained and measured for levels of unacylated ghrelin and acylated ghrelin as well as inflammatory markers and liver and kidney function, electrolytes, and CBC. Blood pressure and pulse will be obtained seated and in the standing position. Brachial artery FMD will be measured and an ECG will be performed. Vitals may be obtained at the discretion of the CRU nurse. Participants will be administered a questionnaire to assess symptoms.

Prior to FMD measures, the participant will be asked to consume a low calorie, low fat meal provided to the participant by CRU nutrition services.

The table below lists timing of the outcome and safety measures.

Measures	Prior to Injection *	30 minutes	60 minutes	90 minutes	3 hours	6 hours	8-12 hours	24 hours
Safety Measures								
Electrocardiogram	X*							X
Comprehensive chemistry panel	X*							X
CBC	X*							X
Pulse and blood pressure	X	X	X	X	X	X	X	X
Orthostatic pulse and blood pressure	X	X	X	X	X	X	X	X

PROTOCOL TITLE: Unacylated Ghrelin to Improve Functioning in PAD: the GIFT Trial

Efficacy outcome measures								
Unacylated and acylated ghrelin levels	X	X	X	X	X	X	X	X
Inflammatory biomarkers	X						X	X
Brachial artery FMD	X					X	X	X

*The ECG, comprehensive chemistry panel (liver and kidney function and electrolytes), and CBC will be obtained at visit #1 for the 10 ug/kg dose.

**The FMD will be performed at either 6 hours or 8-12 hours.

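### The visits at which section 9.2 permits an intravenous sampling line (2, 4 and 6) do not match the serial-sampling visits in section 7.0 (2, 5 and 8)

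*Combined protocol and SAP*

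**What the plan says.** Section 9.2, under Blood collection, says: "At visits 2, 4, and 6 a peripheral intravenous line may be inserted". The same sentence gives the reason: "for the purpose of obtaining blood samples more easily without multiple venipunctures".

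Section 7.0 places the injections elsewhere: "At visits #2, #5, and #8, respectively, participants will receive a subcutaneous injection of unacylated ghrelin of the following doses". The doses follow as "Visit 2: 10ug/kg", "Visit 5: 20 ug/kg" and "Visit 8: 40 ug/kg". The same section sets a pre-injection draw and six post-injection draws on each of these days.

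For two of the remaining visits it says: "At visits 4 and 7, a blood sample will be obtained and tested for liver and kidney function, electrolytes, and CBC". Visit 6 is one of the three follow-up visits held about a day after an injection, and it too has one blood sample.

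**The concern.** A line that spares repeated venipuncture is useful only at a visit with several draws. Of the three visits listed in section 9.2, only visit 2 is of that kind. Visits 4 and 6 are single-sample visits, and visits 5 and 8, which carry the 20 and 40 ug/kg sampling days, are not listed.

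The main stake is burden on the participants. Section 14.0 itself names bruising, inflammation of the vein and infection as risks of drawing blood. A second, less certain stake is sample timing. If the 10 ug/kg day is sampled through a line and the two higher-dose days by separate sticks, the method of sampling differs between doses for no stated reason, and samples on those two days might be taken less punctually. There is also a point of conduct. Section 9.3 describes staff who are certified and re-certified on adherence to the protocol. A visit list that conflicts with the schedule leaves them to choose between following it literally and departing from it without a documented basis.

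**Working it through.** The plan gives no figure to reproduce here, so the check is a count of scheduled blood-sampling times by visit, set against the list in section 9.2.

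**Inputs**
- Visits at which a line is permitted: 2, 4 and 6 (section 9.2).
- Draws on an injection day: 1 before the injection; 5 at 30, 60 and 90 minutes, 3 hours and 6 hours; 1 at 8-12 hours (section 7.0). The timing table in section 7.0 and the Specific Aim in section 1.1 give the same post-injection times.
- Draws at visits 4 and 7: 1 each. Draws at visits 3, 6 and 9: 1 each. Draws at visit 1: 1 (all section 7.0).
- Participants: 6 (section 23.0).

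**Draws per visit**

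| Visit | Role in section 7.0 | Draws | Line named in 9.2 |
|---|---|---|---|
| 1 | Screening | 1 | no |
| 2 | Injection, 10 ug/kg | 1 + 5 + 1 = 7 | yes |
| 3 | 24-hour follow-up | 1 | no |
| 4 | Safety laboratory | 1 | yes |
| 5 | Injection, 20 ug/kg | 7 | no |
| 6 | 24-hour follow-up | 1 | yes |
| 7 | Safety laboratory | 1 | no |
| 8 | Injection, 40 ug/kg | 7 | no |
| 9 | 24-hour follow-up | 1 | no |

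Total per person: 1 + 3 × 7 + 3 × 1 + 2 × 1 = 27 draws, of which 3 × 7 = 21 fall on serial-sampling days. The list in section 9.2 covers 7 of those 21 (visit 2) and leaves 21 − 7 = 14 uncovered (visits 5 and 8).

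**Size under a literal reading**
- Draws by separate venipuncture at visits 5 and 8: up to 7 × 2 × 6 = 84. Of these, 1 × 2 × 6 = 12 are pre-injection draws and 6 × 2 × 6 = 72 are post-injection samples.
- A line at those visits would need its own insertion: 1 × 2 × 6 = 12. The avoidable needle sticks are therefore at most 84 − 12 = 72.
- Cannulations allowed for a single draw at visits 4 and 6: up to 2 × 6 = 12.

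**Is section 9.2 the outlier?** The numbering in section 7.0 agrees with other parts of the protocol. Exclusion criterion 5 in section 3.2 refers to nine visits, and section 22.4 ties payment to visits 3, 6 and 9, the three follow-up visits. No other text in the protocol corrects or explains the list in section 9.2.

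**The case against.** The strongest reply is that the sentence grants permission and gives no instruction. Staff who place no line at visits 4 and 6 comply with it fully, and its stated purpose gives them no reason to place one for a single draw. Nor does it forbid a line at visits 5 and 8; it only fails to name them. Staff working from the section 7.0 schedule would probably notice. This stands. A reader might infer that a line will be placed at visits 4 and 6 and withheld at visits 5 and 8, but the text does not say so, and the counts above can only be upper bounds.

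A reader might also infer that dose selection is compromised, because section 9.1 compares 20 with 40 ug/kg. The documents do not support that. The comparison is offered as an example, selection is among all three doses, and section 9.1 ranks the ghrelin level below brachial artery FMD and oxidative stress. The protocol gives no missed-sample rate, access-failure rate or sampling window, so late or missed samples remain a possibility and no more.

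Finally, the list may be left over from another numbering: with visits 4 and 7 removed, the injection days would become 2, 4 and 6. That is conjecture which the documents do not confirm, and it would explain the mismatch without removing it.

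**Conclusion.** The inconsistency is real, and the current text is wrong as written. Section 9.2 permits the line at two visits where its purpose cannot apply and does not name two of the three visits where it could. Only one of its three listed visits is a serial-sampling visit.

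Taken literally, the size is at most 72 avoidable needle sticks and at most 12 cannulations for single draws across the study. This assumes that all six participants complete every visit, that each draw without a line is one stick, that one insertion serves all seven draws of a day, and that staff follow the list to the letter. Actual numbers could be far smaller, down to none if staff do not follow the list literally.

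The point is minor. It concerns participant burden and possibly sample timing. It changes no estimate, error rate or sample size, and it does not show that the ghrelin profiles or the choice of dose would be biased.

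**What to change.** Reconcile the visit list in section 9.2 (Blood collection) with the visit schedule in section 7.0, so that the two sections agree on the visits at which a sampling line is permitted. Which visits those are is for the investigators to confirm. The consent pages were not available for this review, so any consent text that describes the line should be checked for the same list and aligned if it repeats it.

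The cost is a one-line edit. It calls for no added assessment and no change to the analysis.
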